#### **5.1.2.2** Statistical Methods

Same methods will be used to computed 97.5% CI for seroprotection rate or GMTs.

# 5.1.3 Statistical Methods for Observational Objectives

# **Immunogenicity**

The main parameters for observational objectives are:

Immunogenicity Observational Objective 1:

Descriptive analyses on meningococcal serogroup C measured by hSBA for all subjects in each group will include but not be limited to the following parameters:

- GMTs before and at 30 days (+14 days) after vaccination
- Percentage of subjects with antibody titers  $\geq 1:4$  and  $\geq 1:8$ , assessed at baseline and 30 days (+14 days) after vaccination
- GMT ratio
- Percentage of subjects with a  $\geq$ 4-fold rise from pre-vaccination to post-vaccination
- Vaccine seroresponse rate, with a seroresponse defined as:
  - for a subject with a pre-vaccination titer < 1.8, a post-vaccination titer  $\ge 1.16$
  - for a subject with a pre-vaccination titer ≥ 1:8, a post-vaccination titer at least 4-fold greater that the pre-vaccination titer.
- Distribution titers

*Immunogenicity Observational Objective 2:* 

Descriptive analyses on meningococcal serogroup C measured by rSBA for all subjects in each group will include but not be limited to the following parameters:

- GMTs before and at 30 days (+14 days) after vaccination
- Percentage of subjects with antibody titers ≥ 1:8 and ≥ 1:128, assessed before and at 30 days (+14 days) after vaccination in each group
- GMT ratio
- Percentage of subjects with a ≥4-fold rise from pre-vaccination to post-vaccination
- Vaccine seroresponse rate, with a seroresponse defined as:
  - for a subject with pre-vaccination titer < 1:8, a post-vaccination titer  $\ge 1:32$

• for subjects with pre-vaccination titer ≥ 1:8, a post-vaccination titer at least 4-fold greater that the pre-vaccination titer.

#### • Distribution titers

Descriptive analyses will be done according to each vaccine group. The main parameters will be described with 95% CI using the exact binomial distribution (Clopper-Pearson method) for proportions and using the normal approximation of the Log10 concentrations/titers, followed by a back transformation for GMTs.

Reverse cumulative distribution curves (RCDCs) figures will also be provided for D0 and D30.

Safety Observational Objective:

For safety observational objectives results, the following parameters will be used in each group for the evaluation of safety: counts, percents and 95% CIs of point estimates (calculated using the exact binomial distribution [Clopper-Pearson method]) as well as number of AEs when considered of interest for each of the followings:

- Unsolicited systemic AEs reported in the 30 minutes following the vaccination
- Solicited injection site reactions and systemic reactions starting anytime from D0 through D7 after the vaccination
- Unsolicited non-serious AEs up to D30 after the vaccination
- SAEs (including AESIs) up to D30 after the vaccination and throughout the study, i.e., from D0 to Visit 2

Depending on the items, the parameters could be detailed according to:

Nature (Medical Dictionary for Regulatory Activities [MedDRA] preferred term), time of onset, duration / number of days of occurrence, intensity, relationship to vaccine, whether the AE led to early termination from the study, seriousness criterion, outcome.

# 5.2 Analysis Sets

Four main analysis sets will be used in the study: 2 full analysis set (hSBA FAS and rSBA FAS), 2 per protocol analysis sets (hSBA PPAS and rSBA PPAS) and the safety analysis set (SafAS).

#### 5.2.1 Full Analysis Set

The hSBA FAS is defined as the subset of randomized subjects who received one dose of study vaccine and had a valid post-vaccination serology hSBA result.

The rSBA FAS is defined as the subset of randomized subjects who received one dose of study vaccine and had a valid post-vaccination serology rSBA result.

# 5.2.2 Per-Protocol Analysis Set

The PPAS are subsets of the FAS. The subjects presenting with at least one of the following relevant protocol deviations will be excluded from all PPAS:

- Subject did not meet all protocol-specified inclusion criteria or met at least one of the protocol-specified exclusion criteria.
- Subject did not receive vaccine.
- Subject received a vaccine other than the one that he / she was randomized to receive.
- Preparation and / or administration of vaccine was not done as per-protocol.
- Subject did not provide post-dose serology sample at V02 in the proper time window (i.e., D30+14 days) or the post-dose serology sample was not drawn.
- Subject received a protocol-prohibited Category 2 or Category 3 therapy/medication/vaccine
- Subject had other protocol violations or deviations that affected the subject's immune response, as determined by the clinical team before locking the database.

In addition to the reasons listed above, subjects will also be excluded from the hSBA PPAS if:

2.2) Subject post-dose serology sample at V02 did not produce a valid test result (i.e., hSBA result is missing or not reported)

And from the rSBA PPAS if:

2.3) Subject post-dose serology sample at V02 did not produce a valid test result (i.e., rSBA result is missing or not reported)

This list may not be exhaustive. The above protocol deviations leading to exclusion from the PPAS may be completed if necessary following data review process. The PPAS definition will be finalized before the database lock.

# 5.2.3 Safety Analysis Set

The SafAS is defined as those subjects who have received one dose of study vaccine and have any safety data available.

Safety data recorded for a vaccine received out of the protocol design will be excluded from the analysis and listed separately.

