#### Safety

The safety profile of the 3 vaccines will be evaluated within 30 days (+ 14 days) after the vaccination. The following endpoints will be used for all subjects for the evaluation of safety:

- Unsolicited systemic AEs reported in the 30 minutes following the vaccination
- Solicited (pre-listed in the subject diary and the electronic Case Report Form [CRF])
  injection site reactions and systemic reactions starting anytime from D0 (Day of
  vaccination) through D7 after the vaccination
- Unsolicited (spontaneously reported) non-serious AEs up to from D0 and D30
- SAEs (including AESIs) throughout the study, ie, from D0 to Visit 2

Depending on the items, the endpoints recorded or derived could include:

Nature (Medical Dictionary for Regulatory Activities [MedDRA] preferred term), time of onset, duration / number of days of occurrence, intensity, relationship to vaccine, whether the AE led to early termination from the study, seriousness criterion, outcome.

Planned Sample Size:	A total of 675 subjects were initially planned to be enrolled (with an estimated drop-out rate of 10%).
	• Group 1: MenACYW conjugate vaccine n=225 to be enrolled (202 evaluable)
	• Group 2: Nimenrix® vaccine n=225 to be enrolled (202 evaluable)
	• Group 3: NeisVac-C® vaccine n=225 to be enrolled (202 evaluable)
	As a consequence of the COVID-19 pandemic, enrollment was paused on 17 March 2020.
	Approximately 30 subjects were identified to be excluded from the per-protocol analysis set
	(PPAS) due to COVID-19 as they were unable to complete their follow-up visit as planned per
	the protocol. The sample size of the study will then be modified to replace these subjects.
	Approximately 705 subjects will now be enrolled (235 in each group).
	In the event of any new unexpected situations impacting study visits, the sample size might be
	increased to replace subjects excluded from the PPAS.
Duration of	The duration of each subject's participation in the trial will be approximately 30 to 44 days.
Participation	
in the Study:	
Investigational Product:	MenACYW conjugate vaccine: Meningococcal Polysaccharide (Serogroups A, C, W, and Y) Tetanus Toxoid Conjugate Vaccine (Sanofi Pasteur Inc., Swiftwater, PA, USA)
Form:	Liquid solution
	Each 0.5 mL dose of MenACYW conjugate vaccine is formulated in sodium acetate buffered saline solution to contain the following components:
	Meningococcal capsular polysaccharides:
	Serogroup A10 micrograms (µg)
	Serogroup C
	Serogroup Y

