# 5.2.12 Follow-up of Discontinuations

The site should complete all scheduled safety follow-ups and contact the parent/legally acceptable representative of subject who has prematurely terminated the study because of an AE or a protocol deviation.

For subjects where the reason for early termination was lost to follow-up or if the subject's parent/legally acceptable representative withdrew their informed consent and specified that they do not want to be contacted again and it is documented in the source document, the site will not attempt to obtain further safety information.

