# 12.2.3 Safety Analysis Set

The SafAS is defined as those subjects who have received one dose of study vaccine. All subjects will have their safety analyzed according to the vaccine they actually received.

Safety data recorded for a vaccine received out of the protocol design will be excluded from the analysis (and listed separately).

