#### 4.4.1.1.3 Presence

Presence is derived from the maximum overall intensity on the period considered:

- None: No presence
- Grade 1, Grade 2, or Grade 3: Presence
- Missing: Missing presence

Subjects with at least one non-missing presence for a specific safety endpoint will be included in the analysis. Conversely, those without a non-missing presence will not be included in the analysis of the endpoint.

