#### 4.4.1.2 Unsolicited Non-serious AEs

#### 4.4.1.2.1 Presence

An observation will be considered an event if it has at least a verbatim term and is not a Grade 0 (None) intensity event.

Grade 0 events will not be included in the analysis of the endpoint, and should be included in the listing "Unsolicited non-serious adverse events not included in the safety analysis."

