# **5.2.4** Populations Used in Analyses

The primary immunogenicity analyses will be performed on the hSBA PPAS for comparisons to Nimenrix® and on the rSBA PPAS for comparisons to NeisVac-C® and will be confirmed on the FAS.

The secondary immunogenicity analyses will be performed on the rSBA PPAS for comparisons to Nimenrix® and on the hSBA PPAS for comparisons to NeisVac-C® and will be confirmed on the FAS.

Observational objectives on immunogenicity will be performed on the PPASs and the FAS.

Observational objectives on safety will be performed on the SafAS.

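### Unsolicited AEs have no missing status in the SAP text available, so a vaccinated child with no D0-D30 follow-up is in effect counted as AE-free

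*SAP*

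**What the plan says.** **Safety set.** SAP 5.2.3: "The SafAS is defined as those subjects who have received one dose of study vaccine and have any safety data available". Protocol 12.2.3 has no safety-data condition: "The SafAS is defined as those subjects who have received one dose of study vaccine". SAP 5.2.4 adds: "Observational objectives on safety will be performed on the SafAS". SAP 5.1.3 summarises safety as counts, percentages and exact 95% CIs.

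**Solicited reactions.** SAP 4.4.1.1.3 has three states for a subject: present, not present and missing. It says "Subjects with at least one non-missing presence for a specific safety endpoint will be included in the analysis", and then "Conversely, those without a non-missing presence will not be included in the analysis of the endpoint". There is one exception, in SAP 4.4.1.1.1: if the Investigator recorded No and every daily record is missing, the reaction is set to None (fever excepted).

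**Unsolicited non-serious AEs.** SAP 4.4.1.2.1: "An observation will be considered an event if it has at least a verbatim term and is not a Grade 0 (None) intensity event". This classifies a recorded observation. It gives no status to a subject whose reporting period was not observed.

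**Missing data.** SAP 5.3.1 allows no replacement. Sections 5.3.1.1 to 5.3.1.6 deal with missing attributes of events or daily records: timing, causality, measurement, intensity, dates and action taken.

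**Follow-up.** Parents write unsolicited AEs in the diary card, which is collected and reviewed at Visit 2 (SAP 3.2). Under Protocol 5.2.12, for a child lost to follow-up, or withdrawn with a documented wish for no further contact, "the site will not attempt to obtain further safety information".

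**The concern.** A percentage of children with an unsolicited AE over D0-D30 has a clear meaning only if each child in the denominator could have reported one. The SAP applies that principle to solicited reactions but, in the text available, not to unsolicited AEs. A child who leaves after vaccination with no diary and no later contact still has a 30-minute observation, which would normally count as some safety data. That child would stay in the SafAS and contribute a zero.

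Any resulting error makes the vaccines look safer, never the reverse. If losses differed between arms, the descriptive comparison of the three vaccines would shift as well. The plan asks for no count of unobserved children by arm, so a reader of the report could not tell whether the effect was trivial or material.

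**Working it through.** **1. The plan's own loss figure.** SAP 5.5 assumes 10% drop-out, with 202 evaluable of 225 per group: 225 x 0.90 = 202.5, so it reproduces. It is an allowance for immunogenicity evaluability. No document gives a rate of lost diary cards or of children without D0-D30 follow-up.

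**2. How one unobserved child is scored.**

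| Step | Solicited reactions | Unsolicited non-serious AEs |
|---|---|---|
| In the SafAS? | Yes, given any safety data | Yes, given any safety data |
| Record for D0-D7 or D0-D30? | None | None |
| Status under the SAP | Missing (None if the Investigator recorded No, except fever) | No status defined |
| Effect on the percentage | Generally leaves the denominator | Adds 1 to the denominator, 0 to the numerator |

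**3. Formula.** Let p be the true share of children with an AE, m the share of the SafAS without D0-D30 follow-up, and f the share of those children's AEs captured some other way. If AE risk is the same in followed and unfollowed children:

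reported = p x [1 - m x (1 - f)]

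With f = 0 the relative understatement equals m. All of p, m and f are assumptions.

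**4. Results with f = 0.**

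| m | Basis | p = 10% | p = 30% | p = 50% |
|---|---|---|---|---|
| 2% | assumed | 9.8% | 29.4% | 49.0% |
| 4.3% | all of the approximately 30 COVID-19 children of 705, taken as unobserved | 9.6% | 28.7% | 47.9% |
| 10% | every planned drop-out unobserved (upper case) | 9.0% | 27.0% | 45.0% |

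If half of the AEs are recovered (m = 10%, p = 30%, f = 0.5), the reported figure is 0.30 x 0.95 = 28.5%.

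**5. Interval coverage.** Exact coverage of the 95% Clopper-Pearson interval on n = 235, when only 235 minus u children can report an event:

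| Unobserved per arm (u) | p = 20% | p = 30% | p = 40% |
|---|---|---|---|
| 0 | 95.9% | 95.4% | 96.1% |
| 5 (2.1%) | 95.9% | 95.2% | 95.7% |
| 10 (4.3%) | 95.4% | 94.0% | 93.8% |
| 23 (9.8%) | 91.3% | 85.6% | 81.1% |

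Coverage stays near nominal up to about 10 unobserved children per arm and drops clearly only at the upper case.

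**6. Unequal loss.** At p = 30%, losses of 10% in one arm and 4.26% in another create an apparent difference of 0.30 x (0.10 - 0.0426) = 1.7 points.

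**The case against.** The strongest reply is that nothing in the SAP says an unobserved child is event-free. A reader might take that as the SAP's rule, but it is only a consequence of a SafAS denominator with no missing state. The contents pages list a Section 5 lead-in and Table 5.1 (descriptive statistics), and neither was in the text reviewed, so a denominator rule there cannot be excluded. The SAP also leaves its safety-data condition undefined; that an uneventful 30-minute observation satisfies it is a reasonable reading, not a stated one. Both points stand and make the finding conditional.

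Next, leaving before Visit 2 is not the same as losing the AE data. Staff telephone families who do not return and remind them to send the diary (Protocol 5.1.4.3). The Day 8 call records the child's health status (5.1.4.2), although it cannot cover the days after it. Children terminated for an AE or a protocol deviation continue scheduled safety follow-up (5.2.12). Amendment 1 (5.3.1) allowed telephone safety follow-up during the COVID-19 hold. The exposed group is mainly children lost to follow-up and no-further-contact withdrawals. This also stands, and it limits the size.

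A reader might add the 10% drop-out to the roughly 10 COVID-19 children per arm (33 of 235, 14%) and infer coverage as low as 63% at a true 40%. The documents do not support this. The 10% concerns immunogenicity evaluability. The COVID-19 children were identified as per-protocol exclusions, and Amendment 1 kept in the study those seen out of window. A child can miss the per-protocol set and still have a complete diary.

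It is also tempting to say that the two endpoints always treat such children in opposite ways. The Investigator-No exception in SAP 4.4.1.1.1 shows that they do so only generally.

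None of this supplies the missing status for unsolicited AEs.

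**Conclusion.** The gap is real on the text available: solicited reactions have a subject-level missing state, unsolicited AEs do not, and the missing-data section does not cover an unobserved reporting period. Unless the Section 5 lead-in or Table 5.1 says otherwise, children without D0-D30 follow-up are in effect counted as AE-free, and reported percentages are too low by the relative share of such children.

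That share is unknown. At an assumed true 30%, the shift is 0.6 to 1.3 points for shares of 2% to 4.3%, and 3.0 points in the upper case of 10%. These figures assume equal AE risk in followed and unfollowed children and no capture by other means; capture would shrink them. The likely effect is therefore modest, and material only if nearly all planned drop-outs went unobserved.

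Safety is an observational, descriptive objective, so no hypothesis test or power figure is touched. Distortion between arms would need unequal loss, of which the documents give no evidence. The change is still worth making, because it is cheap and applies a principle the SAP already uses.

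**What to change.** In SAP 4.4.1.2.1 and 5.2.3, before database lock:

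- Flag each SafAS child for documented D0-D30 AE follow-up (diary card reviewed, Visit 2 held, or safety interview by telephone), **irrespective of whether an AE was reported**.
- Give unsolicited-AE percentages and exact CIs on the children with that follow-up, alongside the all-SafAS percentages.
- List AEs from children without complete follow-up, and keep them in the all-SafAS line.
- Show the number without follow-up by arm.
- Align the SafAS definitions in Protocol 12.2.3 and SAP 5.2.3.

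The flag must not depend on the outcome. Scoring as missing only those children who reported no AE would keep lost children with an AE and drop those without. With a true 40%, 10% lost and half of their AEs captured (all assumed), that rule reports (0.36 + 0.02) / (0.90 + 0.02) = 41.3%, against 38.0% on all SafAS.

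The cost is SAP wording and one derived flag. Telephone contacts are recorded on contact forms or in source documents, so some may have to be confirmed there. The denominator becomes slightly smaller and the reported percentages slightly higher. If loss is related to AEs, the followed-up line is not free of bias either, which is why both lines and the counts by arm are needed.

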# **5.2.4** Populations Used in Analyses

The primary immunogenicity analyses will be performed on the hSBA PPAS for comparisons to Nimenrix® and on the rSBA PPAS for comparisons to NeisVac-C® and will be confirmed on the FAS.

The secondary immunogenicity analyses will be performed on the rSBA PPAS for comparisons to Nimenrix® and on the hSBA PPAS for comparisons to NeisVac-C® and will be confirmed on the FAS.

Observational objectives on immunogenicity will be performed on the PPASs and the FAS.

Observational objectives on safety will be performed on the SafAS.

# 5.3 Handling of Missing Data and Outliers

#### **5.3.1** Safety

No replacement will be done. In all subject listings, partial and missing data will be clearly indicated as missing.

#### **5.3.1.1 Immediate**

For unsolicited non-serious systemic AEs, a missing response to the "Immediate" field is assumed to have occurred after the 30-minute surveillance period and will not be imputed.

For SAEs, missing or partially missing elapsed time from last vaccination recorded if within 24 hours will remain missing and not be imputed. Such SAEs will not be considered as immediate.

## 5.3.1.2 Causality

Missing causality (relationship) for unsolicited non-serious AEs and SAEs will be considered at the time of analysis as related to vaccination.

#### 5.3.1.3 Measurements

Partially missing temperatures will be handled as described in Section 4.4.1.1.1

# **5.3.1.4** Intensity

For solicited reactions, missing intensities will be handled as described in Section 4.4.1.1.1. For unsolicited non-serious AEs, missing intensities will remain missing and will not be imputed.

# 5.3.1.5 Start Date and Stop Date

Missing or partially missing start dates for unsolicited AEs will remain missing and not be imputed. If either the start or stop date is missing or partially missing, the time of onset will be considered to be missing. Nevertheless unsolicited AEs with missing time of onset will be included in analyses according to the visit collected.

Missing or partially missing stop dates for AEs (solicited reactions and unsolicited AEs) will remain missing and not be imputed.

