#### **4.4.1.2.4** Time of Onset

Time of onset is derived from the start date of the unsolicited non-serious AE provided in the clinical database and the date of last vaccination:

• start date of the unsolicited non-serious AE – date of vaccination

The time of onset should be considered as missing only if one or both of the dates are missing or partially missing.

The unsolicited non-serious AEs will be analyzed "Within 30 days", which corresponds to AEs with a time of onset between 0 and 30 days after vaccination or missing. An AE with missing time of onset will be considered to have occurred just after the vaccination indicated by the visit number, so will be included in these tables.

Note: Unsolicited non-serious AE that occurred before vaccination (negative time of onset) or with a time of onset higher than defined above (i.e., >30 days after vaccination) will not be included in analysis, but will be listed separately.

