#### 4.4.1.2.5 **Duration**

Duration is derived from the start and stop dates of the unsolicited non-serious AE provided in the clinical database:

• stop date of unsolicited non-serious AE - start date of unsolicited non-serious AE + 1.

The duration should be considered as missing only if one or both of the start and stop dates of the unsolicited non-serious AE is missing or partially missing.

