#### **4.4.1.3.3** Time of Onset

Time of onset will be computed using the same methodology as for unsolicited non-serious AEs described in Section 4.4.1.2.4.

SAEs (including AESIs) will be analyzed throughout the study using the following periods:

- Within 7 days after vaccination
- Within 30 days after vaccination
- During the study period: from D0 to last visit (i.e., all SAEs [including AESIs] occurred during the study)

An SAE (including AESI) with missing time of onset will be considered to have occurred just after the vaccination indicated by the visit number, so will be included in the safety analysis tables.

Note: SAEs (including AESIs) that occurred before vaccination (negative time of onset) will not be included in analysis, but will be listed separately.

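### SAP 5.3.1.5 sets time of onset to missing when only the stop date is missing, against SAP 4.4.1.2.4; if programmed, ongoing late-onset events would move into the early safety tables

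*SAP*

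**What the plan says.** SAP 4.4.1.2.4 defines time of onset for unsolicited non-serious AEs as the start date minus the vaccination date. On missing values it says: "The time of onset should be considered as missing only if one or both of the dates are missing or partially missing". The dates meant are the start date and the vaccination date. An event without an onset is kept and placed early: "An AE with missing time of onset will be considered to have occurred just after the vaccination indicated by the visit number". Events with a known onset before vaccination or more than 30 days after it are left out of the analysis and listed.

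SAP 4.4.1.3.3 carries this over to SAEs and AESIs: "Time of onset will be computed using the same methodology as for unsolicited non-serious AEs described in Section 4.4.1.2.4". It reports them in three periods (7 days, 30 days, whole study) and repeats both conventions: "An SAE (including AESI) with missing time of onset will be considered to have occurred just after the vaccination indicated by the visit number", and "SAEs (including AESIs) that occurred before vaccination (negative time of onset) will not be included in analysis, but will be listed separately".

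SAP 4.4.1.2.5 is where the stop date enters: "The duration should be considered as missing only if one or both of the start and stop dates" are incomplete.

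SAP 5.3.1.5 then gives a different rule for onset: "If either the start or stop date is missing or partially missing, the time of onset will be considered to be missing". It adds that unsolicited AEs without an onset are analysed by the visit at which they were collected, and that stop dates are not filled in: "Missing or partially missing stop dates for AEs (solicited reactions and unsolicited AEs) will remain missing and not be imputed". The footnote on stop dates in Protocol 9.3.2.3.3 treats an AE that never received a stop date as ongoing at study end.

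**The concern.** Two sections of the SAP give different missing-data rules for the same derived variable, and neither is said to take precedence. They part company when the start date is known and the stop date is missing or partial. Every event still ongoing at study end is in that state.

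Since missing onset is converted into onset just after vaccination, the 5.3.1.5 rule would discard a known date and replace it with the earliest possible one. Two programmers working from this SAP could produce different 7-day and 30-day safety tables from the same data. Under 5.3.1.5, an AESI such as a seizure or Guillain-Barré syndrome with a documented start in week 4 and no stop date would be shown as falling within a week of vaccination.

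**Working it through.** The plan states no figure to reproduce. The check is to apply each rule to the same records and see where the results differ.

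**Inputs.** Onset = start date − vaccination date (SAP 4.4.1.2.4). Missing onset is counted as just after vaccination (SAP 4.4.1.2.4 and 4.4.1.3.3). The term unsolicited AE covers serious and non-serious events (Protocol 9.3.2.1), so 5.3.1.5 reaches SAEs. There is one vaccination, at V01 (SAP 4.4.1.2.3 and 4.4.1.3.2). V02 falls on D30 to D44. Parents are told to record events over 30 (+14) days (Protocol 9.3.2.3.3), so onset after D30 can be recorded.

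**Records with vaccination on D0, start date known, stop date missing:**

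| Event | Under 4.4.1.2.4 / 4.4.1.3.3 | Under 5.3.1.5 |
|---|---|---|
| SAE starting D20 | Onset 20; 30-day and study tables | Onset missing; also in the 7-day table |
| SAE starting D35 | Onset 35; study table only | Onset missing; also in the 7-day and 30-day tables |
| Non-serious AE starting D20 | Onset 20; 30-day table | 30-day table, but onset lost |
| Non-serious AE starting D35 | Onset 35; excluded and listed | Onset missing; in the 30-day table |
| Any event starting before vaccination | Negative onset; excluded and listed | Onset missing; included |

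For ongoing non-serious AEs starting D0 to D30, membership of the 30-day table is the same under both rules and only the onset value is lost. Immediate AEs are identified by a separate field (SAP 5.3.1.1), and onset of solicited reactions comes from daily intensities (SAP 4.4.1.1.4); neither is affected.

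**How much of follow-up is exposed.** Assume, for illustration, that onset is uniform over the days from D0 to V02.

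- Onset after D7, V02 at D30: D8–D30 is 23 of 31 days, 23/31 = 74%.
- Onset after D7, V02 at D44: D8–D44 is 37 of 45 days, 37/45 = 82%.
- Onset after D30, V02 at D30: 0/31 = 0%.
- Onset after D30, V02 at D44: D31–D44 is 14 of 45 days, 14/45 = 31%.

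These are shares of onset days, not of misplaced events; an event moves only if it also lacks a complete stop date.

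**Scale of SAEs.** Protocol 1.2.1.2 reports 7 subjects with 11 SAEs among 918 randomized in MET51. Assuming the same rate:

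- subjects: 7/918 × 705 = 5.4
- SAEs: 11/918 × 705 = 8.4

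That is about 5 subjects with about 8 SAEs over three arms. The documents do not give MET51's follow-up length, so this indicates order of magnitude only.

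**The case against.** The strongest reply is that the SAP leans towards the correct rule. Section 4.4.1.2.4 is the dedicated derivation section, its wording is exclusive, and 4.4.1.3.3 points to it for SAEs without mentioning 5.3.1.5. A programmer who works from section 4 gets the right answer, and the sentence in 5.3.1.5 looks like the duration condition put in the wrong place. This is fair as a prediction of what would be programmed, but it does not remove the conflict: 5.3.1.5 is the section on missing dates, it is explicit, and nothing subordinates it.

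Second, 5.3.1.5 has its own handling, by visit collected, and does not itself assign events to the 7-day table. That is correct. The early placement comes from 4.4.1.2.4 and 4.4.1.3.3. But the only vaccination is at V01, so the visit wording offers no other vaccination to attach the event to, and the convention in those two sections still applies.

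Third, the reach is narrow. Most of the protocol limits unsolicited AE recording to D0–D30. Pre-existing conditions are not reported as AEs (Protocol 9.3.2.1), and consent, first blood draw and vaccination normally fall on one visit, so ongoing events with negative onset should be rare. Stop dates of related AEs are actively sought. All of this stands, and it limits the expected number of events rather than the validity of the point.

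**Conclusion.** The contradiction is real and 5.3.1.5 is wrong as written: the stop date plays no part in calculating onset. If that section is the one programmed, the 7-day and 30-day SAE/AESI tables and, to a lesser degree, the 30-day non-serious AE table would hold events whose recorded start dates place them elsewhere. If 4.4.1.2.4 is programmed, none of this happens.

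The size is unknown, because the documents give no count of events without a stop date; it may be zero. With SAEs expected in single figures, even one misplaced event would be visible in an arm's count. That expectation rests on the MET51 rate carrying over. The whole-study SAE table would change only for ongoing events that began before vaccination. Safety is an observational objective, so no hypothesis test, sample size or immunogenicity conclusion is affected. It should be corrected, mainly because the safety tables ought not to depend on which section the programmer reads.

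**What to change.** Replace the onset sentence in SAP 5.3.1.5 with: *If the start date or the vaccination date is missing or partially missing, the time of onset will be considered missing; a missing or partial stop date affects only duration.* This agrees with SAP 4.4.1.2.4 and 4.4.1.2.5 and needs no change elsewhere.

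The cost is one sentence before database lock, with no new data. If the database is already locked, the study report should state which rule was programmed.
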